Date: February 1st, 2022

Study Protocol and Statistical Analysis Plan

Study Title	A Novel, Non-pharmacological, Intervention for the Management of ADHD in Adolescents
Protocol ID	VIZO_004
ClinicalTrials.gov ID	NCT05835336

Protocol Synopsis

Device Name	VIZO Glasses
Objectives	To Assess the Efficacy and Safety of a Novel Device (VIZO Glasses) in the Management of ADHD in Adolescents.
Study Group Investigational Group	VIZO Glasses: Eyeglasses with personalized peripheral retinal stimuli
Key Eligibility Criteria	
Inclusion Criteria	
 • Documented history of primary ADHD diagnosis by certified clinicians • Age 12-17 y • Minimum total of 24 on the parent ADHD-IV Rating Scale (ADHD-RS) • Written informed consent • Able and willing to complete all required ratings and assessments
Exclusion Criteria	
 • Any current psychiatric/neurological comorbidity (e.g., epilepsy, Autism, depression, TBI, etc.), other than ADHD • ADHD Medications (stimulants, non-stimulants, other) • Undergoing Neurofeedback, cognitive training • Any other reason that, in the opinion of the investigator, prevents the participant from participating in the study
Endpoints	
Primary	
Primary Outcome Measure: Change in the ADHD Rating Scale (ADHD-RS) Parent-report Questionnaire - Total Score [Time Frame: Baseline, 2-month]
 
The ADHD-RS is a parent report questionnaire that is used to aid in the diagnosis of ADHD in children ranging from ages 5-17. The questionnaire contains 18 symptom items corresponding to the DSM-V criteria for ADHD. The parent rates each symptom item on a 4-point Likert scale ranging from 0 ('Never or Rarely') to 3 ('Very Often'). The total score goes from 0 up to 54. Higher scores mean more symptoms and higher ADHD impairments.
 
Change in the ADHD Rating Scale (ADHD-RS) Parent-report Questionnaire - Inattention Subscale [Time Frame: Baseline, 2-month]
 
The Inattention subscale of the ADHD-RS contains 9 symptom

Protocol Synopsis

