	
items, that are designed to measure the child's attention level on tasks or play activities. The items are rated by the parent on a 4-point Likert scale ranging from 0 ('Never or Rarely') to 3 ('Very Often'). The total score goes from 0 up to 27. Higher scores mean more symptoms and higher ADHD impairments.
 
Change in the ADHD Rating Scale (ADHD-RS) Parent-report Questionnaire - Hyperactivity-Impulsivity Subscale [Time Frame: Baseline, 2-month]
 
The Hyperactivity-Impulsivity subscale of the ADHD-RS contains 9 symptom items, that are designed to measure the child's hyperactivity level and impulsivity level. The items are rated by the parent on a 4-point Likert scale ranging from 0 ('Never or Rarely') to 3 ('Very Often'). The total score goes from 0 up to 27. Higher scores mean more symptoms and higher ADHD impairments.
 
Change in Behavior Rating Inventory of Executive Function (BRIEF) - Metacognitive Index [Time Frame: Baseline, 2-month]
 
The Metacognition Index (MI) of the BRIEF reflects a child's ability to self-manage and monitor tasks cognitively. The subscale is composed of the Initiate, Working Memory, Plan/Organize, Organization of Materials, and Monitor scales of the BRIEF. It uses a Likert-type response format ranging from 1 to 3, where 1 is never, 2 is sometimes, and 3 is often. High scores indicate executive deficit.

Secondary	
Secondary Outcome Measures:
 
Clinical Global Impression-Improvement (CGI-I) [Time Frame: 2-month]
 
Based on an interview with the participant, the clinician rates the total improvement on a 7 point scale as follows: 1=very much improved since the initiation of treatment; 2=much improved; 3=minimally improved; 4=no change from baseline (the initiation of treatment); 5=minimally worse; 6= much worse; 7=very much worse since the initiation of treatment.
 
Change in Behavior Rating Inventory of Executive Function (BRIEF) - Global Executive Composite [Time Frame: Baseline, 2-month]
 
The BRIEF is a standardized measure that captures views of

Protocol Synopsis

	executive functions or self-regulation in the everyday environment. The BRIEF is composed of 86 items, where each item is rated by the parent, using a 3-point Likert scale ranging from 1 ('Never') to 3 ('Often'). The Global Executive Composite (GEC) is an overarching summary score that incorporates all of the BRIEF clinical scales. High scores indicate executive deficit.

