Other Outcomes	Adverse events will be monitored and documented.
Follow-up Visits Schedule	This was a two-month, open-label study in which eligible ADHD-diagnosed adolescents were provided with a pair of VIZO-Glasses featuring a personalized visual stimuli pattern for each participant. A baseline assessment of the participants' ADHD clinical profile pre-intervention included the ADHD-RS and the Behavior Rating Inventory of Executive Function (BRIEF) questionnaires. In addition, participants completed the Conners' Continuous Performance Test-3 (CPT-3). Optical centration parameters and demographic information were collected for each participant. Participants were then invited to complete a personalization process in which they were fitted with personalized VIZO-glasses. Participants were instructed to wear their Vizo-glasses for at least two hours daily for two months. A follow-up assessment at the end of the intervention re-assessed ADHD performance on the ADHD-RS and BRIEF questionnaires. In addition, participants completed the CPT-3 test while wearing their VIZO-glasses. The Clinical Global Impression-Improvement (CGI-I) rating scale was administered by a clinician.
Sample Size	Given the exploratory nature of the study, the sample size was chosen to be sufficiently large to detect significant within subject effects of at least 0.5 (Cohen's D) for a 2-Tailed test, at $\alpha=0.05$ with a power of 80%.
Analysis Plan	Paired samples t-tests will be used to test the effect of the VIZO-glasses intervention, comparing the baseline and end-of-intervention performances. No corrections for multiple testing will be applied due to the exploratory nature of the study. The safety analysis will include all available data on the intent-to-treat (ITT) population.

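### Do four uncorrected primary changes, with no lead endpoint named, require a change to the plan?

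*Combined protocol and SAP*

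**What the plan says.** The synopsis has one row for primary and one for secondary endpoints. The primary row opens with "Primary Outcome Measure: Change in the ADHD Rating Scale (ADHD-RS) Parent-report Questionnaire - Total Score" (range 0 to 54). In the same row and format it goes on to the Inattention subscale (0 to 27), the Hyperactivity-Impulsivity subscale (0 to 27) and the BRIEF Metacognitive Index, all measured at baseline and two months. The secondary row, headed "Secondary Outcome Measures", holds the CGI-I and the BRIEF Global Executive Composite.

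The Analysis Plan row specifies paired t-tests without naming an endpoint and adds: "No corrections for multiple testing will be applied due to the exploratory nature of the study". The Sample Size row begins "Given the exploratory nature of the study, the sample size was chosen to be sufficiently large" and continues with a within-subject Cohen's d of at least 0.5, a two-tailed test, alpha 0.05 and 80% power. It names no endpoint and states no number of participants. No ranking, test order or success rule for the four changes appears anywhere.

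**The concern.** A primary tier normally tells the reader which result decides the study. Here four results share it, each tested at 0.05, and two of them are components of a third. With no lead endpoint and no rule such as any, all or a named one, a significant subscale or BRIEF result could be put forward as the primary finding while the Total is not significant.

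The power statement raises a related question. If d = 0.5 was meant for the Total, the subscales may have less than 80% power. If it was meant for the subscales, the Total may have more. The label before the Total is singular and the secondary heading is plural, which may hint that the Total leads. But the other three changes sit under the same label, so it may equally be a list heading.

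The stated objective is to assess efficacy and safety, and the sample size is framed around detecting significant effects. So the exploratory label is not the plan's only signal of intent.

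**Working it through.** **Inputs.** From the Sample Size row: d = 0.5, two-sided alpha 0.05, power 80%. From the endpoint table: four changes, with the ADHD-RS Total being the sum of its two subscales. The documents give no sample size, standard deviations, mean changes or correlations. Those used below are assumptions.

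**Implied sample size.** There is no stated figure to reproduce. The normal approximation gives n = ((1.960 + 0.842)/0.5)² = 31.4, so 32 pairs. The exact paired t calculation gives 33.4, so 34 pairs: power is 79.5% at n = 33 and 80.8% at n = 34. I use n = 34.

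**Chance of a false finding.** Four independent tests would give 1 − 0.95⁴ = 18.5%. Independence cannot hold, because the Total is built from two of the others. The rates below come from simulating 34 pairs per trial (1,000,000 trials per setting), with no true mean change, equal subscale SDs, Total = Inattention + Hyperactivity-Impulsivity, and a common correlation r between the three component changes.

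| Event | r = 0.2 | r = 0.5 | r = 0.8 |
|---|---|---|---|
| At least one of four significant, either direction | 15.2% | 13.2% | 10.1% |
| At least one of four significant, benefit direction | 7.7% | 6.6% | 5.0% |
| ADHD-RS subscale shows benefit, Total does not | 3.0% | 2.4% | 1.5% |
| Subscale or BRIEF index shows benefit, Total does not | 5.2% | 4.1% | 2.5% |

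About half of the first row is false worsening, which nobody would present as success, so the second row is the relevant one. It should be compared with 2.5% for a single endpoint. The rows agree with each other: 2.5% for the Total plus the last row gives 7.7%, 6.6% and 5.0%. The two-sided rate hardly depends on n: it is 15.3/13.3/10.1% at n = 20 and 15.3/13.2/10.0% at n = 48.

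**What the power statement implies.** Suppose d = 0.5 refers to the Total and the subscales have equal SDs and equal mean changes. Each subscale then has d = 0.5 × √(2 + 2r)/2:

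- r = 0.2: 0.5 × 1.549/2 = 0.387, power 59% at n = 34
- r = 0.5: 0.5 × 1.732/2 = 0.433, power 69%
- r = 0.8: 0.5 × 1.897/2 = 0.474, power 77%

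This is conditional on equal mean changes. With equal SDs and r = 0.5, subscale effects of 0.60 and 0.27 give a Total effect of (0.60 + 0.27)/√3 = 0.50. The stronger subscale then has 92% power, more than the Total's 81%. So it cannot be said that the subscales must fall below 80%.

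**What correction would cost.** Bonferroni at 0.05/4 = 0.0125 would need 48 pairs for 80% power at d = 0.5. At 34 pairs, power would be 61%.

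**The case for a change.** The best argument for a change is that it is cheap and the gap is real. The plan keeps a primary tier and sizes the study for significance, but does not say what counts as a primary result. One sentence would settle it: either the Total leads and the power statement refers to it, or all four changes are descriptive. Neither option adds participants or reduces power for the Total. The facts behind this argument stand.

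It does not show that the plan goes wrong if followed. All four changes are declared primary, so following the plan means reporting all four. Singling out one would be selective reporting against the plan's own list, and any reader could see it. The descriptive wording would largely restate what the exploratory label already conveys.

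Naming the Total means demoting three declared primaries, a choice on which reasonable statisticians would differ. Entry requires a minimum ADHD-RS total of 24, so the Total may be the change most exposed to regression to the mean if the screening score also serves as baseline, which is not stated. The synopsis also describes conduct in the past tense, so a lead endpoint might no longer be a genuine pre-specification.

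The Sample Size row speaks of effects in the plural. It can fairly be read as a detectable size for any of the paired tests, and on that reading nothing depends on which endpoint was meant.

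**Conclusion.** No change is needed. The plan leaves unwritten which of the four changes leads, or that none does, but it openly declines multiplicity correction and twice describes itself as exploratory. For a study of this kind, four uncorrected tests, all reported, are a fair trade-off: Bonferroni would raise the implied sample size from 34 to 48 pairs.

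The extra risk of a false benefit claim is modest: 7.7%, 6.6% or 5.0% for any of the four against 2.5% for one, and 1.5% to 3.0% for an ADHD-RS subscale without the Total. These figures assume 34 pairs, equal subscale SDs, common correlations of 0.2 to 0.8 and no true mean change. That last assumption is itself doubtful. In a single-arm, open-label study with a minimum entry score, the mean may shift through expectancy or regression to the mean even if the device does nothing, and naming a lead endpoint would not cure that.

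An analyst can fill the gap sensibly by reporting all four mean changes with 95% confidence intervals and claiming no primary success from any one alone.
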